11.1.6.1. Hypotheses

The following hypotheses will be used to evaluate the sensed amplitude Secondary Effectiveness Endpoint 1 [REDACTED]:

H₀: The three -month mean R-wave amplitude is ≤ 3.0 mV

H_a: The three -month mean R-wave amplitude is > 3.0 mV

11.1.6.2. Sample Size

[REDACTED]

[REDACTED]:

- [REDACTED]
- [REDACTED]

December 17, 2013
FINAL

Boston Scientific
NAVIGATE X4 Study Protocol
90874504 Version AB
Page 52 of 101

- [REDACTED]
- [REDACTED]

[REDACTED]

11.1.6.3. Statistical Methods

ACUITY X4 Secondary Effectiveness Endpoint 1 will be analyzed when the last 3-month [REDACTED] follow-up visit is complete. This analysis will include [REDACTED] subjects with an ACUITY X4 LV sensed amplitude measurement at three months, and the analysis will be done [REDACTED] [REDACTED] Sensed amplitude measurements in the programmed configuration from the three-month follow-up visit will be analyzed using a one-sided t-test with an alpha of 2.5%. A histogram of three month LV sensed amplitudes in the programmed configuration will also be provided.

11.1.7. ACUITY X4 Secondary Effectiveness Endpoint 2

The second secondary effectiveness endpoint for ACUITY X4 is pacing impedances in the programmed configuration. This endpoint will be evaluated at 3 months post-implant.

11.1.7.1. Hypotheses

The following hypotheses will be used to evaluate the pacing impedance Secondary Effectiveness Endpoint for [REDACTED]:

H₀: The three -month mean LV lead impedance is ≤ 300 Ω

H_a: The three -month mean LV lead impedance is > 300 Ω

11.1.7.2. Sample Size

[REDACTED]
[REDACTED]:

- [REDACTED]
- [REDACTED]
- [REDACTED]
- [REDACTED]

[REDACTED]

11.1.7.3. Statistical Methods

ACUITY X4 Secondary Effectiveness Endpoint 2 will be analyzed when the last 3-month follow-up visit [REDACTED] is complete. This analysis will include all [REDACTED] patients with an ACUITY X4 LV pacing impedance at three months, and the analysis will be done [REDACTED] LV lead pacing impedance measurements in the programmed configuration from the three-month follow-up visit will be analyzed using a one-

December 17, 2013
FINAL

Boston Scientific
NAVIGATE X4 Study Protocol
90874504 Version AB
Page 53 of 101

sided t-test with an alpha of 2.5%. A histogram of three month LV pacing impedances in the programmed configuration will also be provided.

11.1.8. ACUITY X4 Ancillary Analyses

11.1.8.1. ACUITY X4 Ancillary Safety Objective

The ACUITY X4 Ancillary Safety Objective will be used to prospectively determine the chronic five year complication-free rate of the ACUITY X4 LV lead. [REDACTED]

[REDACTED]

11.1.8.2. ACUITY X4 Ancillary Data Collection

The following data will be collected and summarized:

- Implant success
- Lead measurements in all tested configurations
- Dislodgment rate (post-implant)
- Skin-to-skin time
- Feedback from the site investigator regarding final ACUITY X4 programmed configuration if the physician chooses a configuration other than the best configuration; (best electrode is the one that has the lowest threshold without phrenic nerve stimulation (PNS). In the event of a “tie” for best electrode, the investigator should use their medical judgment to select the best)
- ACUITY X4 Lead placement time
- Interoperative repositioning and rationale for selection of multiple veins/branches
- Method of lead delivery (inner or outer sheath)
- Vein used to implant LV lead – Right-sided vs. left-sided and axillary, cephalic, or subclavian

11.2. RELIANCE 4-FRONT Endpoints

11.2.1. RELIANCE 4-FRONT Primary Safety Endpoint 1

Safety of the RELIANCE 4-FRONT Leads will be evaluated by the lead-related complication-free rate (CFR) from lead implant through the 3-month follow-up visit, based on complications that are related to the RELIANCE 4-FRONT Lead. Lead-related complications are defined as lead-related adverse events resulting in permanent loss of pacing therapy, invasive intervention, injury or death. Lead-related adverse events are further defined in Section 19.3 and lead-related complications are further defined in Section 19.3.1.

December 17, 2013
FINAL

Boston Scientific
NAVIGATE X4 Study Protocol
90874504 Version AB
Page 54 of 101

Lead-related complications associated with attempted RELIANCE 4-FRONT Lead implants will count toward this safety endpoint.

11.2.1.1. Hypotheses

The following hypotheses will be used to evaluate the RELIANCE 4-FRONT Primary Safety Endpoint 1 [REDACTED]:

H₀: The lead-related complication-free rate from implant to 3 months ≤ 93.0%

H_a: The lead-related complication-free rate from implant to 3 months > 93.0%

[REDACTED]

11.2.1.2. Sample Size

[REDACTED]

- [REDACTED]
- [REDACTED]
- [REDACTED]
- [REDACTED]
- [REDACTED]

[REDACTED]

11.2.1.3. Statistical Methods

Data from all subjects implanted or attempted with a RELIANCE 4-FRONT lead will be eligible for inclusion in the endpoint analysis. All RELIANCE 4-FRONT leads [REDACTED] will be pooled for this analysis.

The lead-related complication-free rate from date of implant (or date of attempt, for leads attempted but not implanted) through 91 days post-implant will be calculated using Kaplan-Meier methodology. The 95% one-sided lower pointwise confidence limit of the complication-free rate will be calculated via log-log methodology for all eligible subjects contributing to the analyses and compared to the performance goal of 93%. If the lower confidence limit exceeds 93%, the null hypothesis will be rejected.

Each lead's exact follow-up time in the 91 days post-implant will be included in the analysis via Kaplan-Meier methodology. The leads that fail to reach 91 days of follow-up (without

December 17, 2013
FINAL

Boston Scientific
NAVIGATE X4 Study Protocol
90874504 Version AB
Page 55 of 101

experiencing an endpoint event prior to their end of follow-up in the period) will be censored at the time of their end of follow-up in the period. Because non-informative censoring cannot be assumed for these leads, a tipping point analysis will be performed to determine the potential effects these censored leads could have on the results if full information on each lead was present. The tipping point analysis will assign each lead that was censored prior to 91 days as either having or not having an endpoint event. The tipping point will be determined by the point at which the endpoint results turn from passing (null hypothesis) to failing (null hypothesis rejected). An exact binomial test will be performed for the tipping point analysis.

11.2.2. RELIANCE 4-FRONT Primary Safety Endpoint 2

To satisfy the safety assessment requirements of the US Food and Drug Administration (FDA), safety of the RELIANCE 4-FRONT Leads will also be evaluated by the lead-related CFR from three months post-implant through 24 months post implant based on complications that are related to the RELIANCE 4-FRONT Lead during that period. The same definition of lead-related complication will be used for both RELIANCE 4-FRONT Primary Safety Endpoint 1 and Primary Safety Endpoint 2.

11.2.2.1. Hypotheses

The following hypotheses will be used to evaluate RELIANCE 4-FRONT Primary Safety Endpoint 2 [REDACTED]:

H₀: The lead-related complication-free rate from 3 to 24 months ≤ 94%

H_a: The lead-related complication-free rate from 3 to 24 months > 94%

11.2.2.2. Sample Size

[REDACTED]

- [REDACTED]
- [REDACTED]
- [REDACTED]
- [REDACTED]
- [REDACTED]

[REDACTED]

11.2.3. Statistical Methods

Data from all RELIANCE 4-FRONT leads that have been followed for at least [REDACTED] days post-implant at the time of endpoint analysis will be eligible for inclusion in the endpoint analysis. All RELIANCE 4-FRONT leads [REDACTED] will be pooled for this analysis.

December 17, 2013
FINAL

Boston Scientific
NAVIGATE X4 Study Protocol
90874504 Version AB
Page 56 of 101

The lead-related complication-free rate from [redacted] days through [redacted] days post-implant will be calculated using Kaplan-Meier methodology. The 95% one-sided lower pointwise confidence limit of the complication-free rate will be calculated via log-log methodology for all eligible subjects and compared to the performance goal of 94%. If the lower confidence limit exceeds 94%, the null hypothesis will be rejected.

Each lead’s exact follow-up time in the period between [redacted] days post-implant will be included in the analysis due to the rate being calculated via Kaplan-Meier methodology. The leads that reach [redacted] of follow-up but fail to reach [redacted] of follow-up (without experiencing an endpoint event in the period prior to their end of follow-up) will be censored at the time of their end of follow-up in the period. Because non-informative censoring cannot be assumed for these leads, a tipping point analysis will be performed to determine the potential effects these censored leads could have on the results if full information on each lead was present. The tipping point analysis will assign each lead that was censored between the [redacted] [redacted] post-implant as either having or not having an endpoint event. The tipping point will be determined by the point at which the endpoint results turn from passing (null hypothesis) to failing (null hypothesis rejected). An exact binomial test will be performed for the tipping point analysis.

11.2.4. RELIANCE 4-FRONT Secondary Safety Endpoint

The purpose of this endpoint is to confirm that the RELIANCE 4-FRONT lead and its associated PG system have the ability to appropriately sense and detect VT/VF. Historically, this endpoint has been used to evaluate system performance; the lead is part of the system and therefore will be evaluated in this study. Subjects will not be required to undergo induction testing. Those subjects with a RELIANCE 4-FRONT lead that undergo induction testing within 30 days of implant, per the discretion of the investigator, will be included in the analysis and the time to detection of VT/VF will be measured.

11.2.4.1. Hypotheses

The time it takes for the device to detect VT/VF will be compared to performance goal of 4.5 seconds, [redacted]

[redacted]

H₀: Induced mean VT/VF detection time ≥ 4.5 seconds

H_a: Induced mean VT/VF detection time < 4.5 seconds

11.2.4.2. Sample Size

[redacted]

- [REDACTED]
- [REDACTED]
- [REDACTED]
- [REDACTED]
- [REDACTED]

[REDACTED]

11.2.4.3. Statistical Methods

Data from all subjects with a RELIANCE 4-FRONT lead that have undergone an induction test within 30 days of implant will contribute to the analysis of this endpoint.

If multiple tests or multiple configurations are tested in the 30 day post-implant period, the last induction test in its final configuration will be used in the analysis. A one-sided one-sample t-test will be performed, using an alpha equal to [REDACTED]. If the t-test is deemed to be inappropriate based on the data, then a data transformation or a non-parametric test will be performed. If the p-value for the one-sided test is less than [REDACTED], the null hypothesis will be rejected.

11.2.5. RELIANCE 4-FRONT Primary Effectiveness Endpoint

Effectiveness of the RELIANCE 4-FRONT Leads will be established by demonstrating that the leads provide clinically acceptable pacing thresholds at a 0.5 ms pulse width at three months post implant. [REDACTED].

11.2.5.1. Hypotheses

The following hypotheses will be used to evaluate the RELIANCE 4-FRONT Primary Effectiveness Endpoint [REDACTED]:

H₀: The pacing threshold at 0.5 ms at three months post-implant \geq 1.5 V

H_a: The pacing threshold at 0.5 ms at three months post-implant $<$ 1.5 V

11.2.5.2. Sample Size

[REDACTED]

- [REDACTED]
- [REDACTED]
- [REDACTED]
- [REDACTED]
- [REDACTED]

[REDACTED]

11.2.8. RELIANCE 4-FRONT Secondary Effectiveness Endpoint 3

The purpose of this secondary endpoint is to confirm that the RELIANCE 4-FRONT lead and its associated PG system have the ability to successfully convert VT/VF. Historically, this endpoint has been used to evaluate system performance; the lead is part of the system and therefore will be evaluated in this study. Subjects will not be required to undergo induction testing. Those subjects that undergo induction testing within 30 days of implant, per the discretion of the investigator, will be included in the analysis and the time to detection of VT/VF will be measured. Success will be considered if the device converts the subject's last induced episode in its final configuration without the need for external defibrillation.

11.2.8.1. Hypotheses

The percent of successful VT/VF conversions with a RELIANCE 4-FRONT lead will be compared to a performance goal of 93%, [REDACTED]. The null hypothesis will therefore be rejected in favor of the alternative if the upper confidence limit of the observed percent of successful conversions is greater than 93%. The conversion will be considered successful if the device converts the subject without the need for external defibrillation. [REDACTED]

[REDACTED]

H₀: Percent of successful conversion ≤ 93%

H_a: Percent of successful conversion > 93%

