10.5.12. Optional Ventricular Tachyarrhythmia Induction

Subjects are not required to undergo induction testing. Those subjects that undergo induction testing within 30 days of implant, per the discretion of the investigator, will be included in the analysis of the 4-FRONT Secondary Safety Endpoint and the 4-FRONT Secondary Effectiveness Endpoint 3. See Sections 11.2.4 and 11.2.8, respectively, for more information on these endpoints. The method of induction is per the physician's discretion but BSC strongly recommends the programmer/ PRM electrogram be run continuously during induction and delivery of therapy. VT/VF will be induced and the device allowed to sense and detect the arrhythmia (VT/VF Detection Time) and deliver programmed therapy (VT/VF Shock Conversion). The investigator shall allow the device to deliver at least one shock prior to external rescue, if appropriate. If multiple shock lead configurations (different shock vectors, polarities or lead positions) are tested, data from the final configuration must be used to document both detection time and shock conversion. VT/VF Detection Time is defined as the interval starting 250 ms after the last induction artifact (the time of the post induction ventricular refractory period) and ending at the "V-Episode Declared" marker. Programming of detection and duration should remain at nominal settings .

Steps for VT/VF induction:

1. Run programmer/PRM paper
2. Induce VT/VF
3. Allow device to sense and detect arrhythmia. Measure and record detection time.
4. Allow device to deliver therapy. Record conversion efficacy from final configuration.

If not done at implant, the physician may complete the optional VT/VF induction testing at pre-discharge or within 30 days of implant (at an additional follow up). Subjects may have additional VT/VF testing done if deemed appropriate.

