11.1.3. Statistical Methods

To assess safety of the ACUITY X4 leads, the Kaplan-Meier six month (180-day) complication-free rate will be calculated. [redacted]
The analysis will be conducted when the last 6-month follow-up is completed [redacted]
[redacted] Data from all implanted or attempted [redacted] [redacted] leads will be included in the endpoint analysis.

December 17, 2013
FINAL

Boston Scientific
NAVIGATE X4 Study Protocol
90874504 Version AB
Page 49 of 101

[REDACTED]

The exact follow-up time for each ACUITY X4 lead in the 180-day post-implant period will be included in the analysis via Kaplan-Meier methodology. The leads that fail to reach 180 days of follow-up (without experiencing an endpoint event prior to their end of follow-up in the period) will be censored at the time of their end of follow-up in the period. Because non-informative censoring cannot be assumed for these leads, a tipping point analysis will be performed to determine the potential effects these censored leads could have on the results if full information on each lead was present. The tipping point analysis will assign each lead that was censored prior to 180 days as either having or not having an endpoint event. The tipping point will be determined by the point at which the endpoint results turn from passing (null hypothesis) to failing (null hypothesis rejected). An exact binomial test will be performed for the tipping point analysis.

11.1.4. ACUITY X4 Primary Effectiveness Endpoint 1

The first effectiveness endpoint for ACUITY X4 is pacing capture thresholds (PCT) in the programmed configuration. This endpoint will be evaluated at 3 months post-implant. [REDACTED] For this endpoint, responders will be defined as subjects with $PCT \leq 2.5$ V in the programmed configuration.

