11.2.8.3. Statistical Methods

All subjects with a RELIANCE 4-FRONT lead that undergo an induction test within 30 days of implant will contribute to the analysis of this endpoint. If multiple tests or multiple configurations are tested in the 30 day post-implant period, the last induction test in its final configuration will be used in the analysis. A one-sided exact binomial test will be performed on all subjects with induction data (regardless of lead fixation or coil type) and the resulting lower exact (Clopper-Pearson) confidence interval will be calculated, using an alpha equal to █%. If the lower one-sided 95% confidence limit for the conversion rate is greater than 93%, the null hypothesis will be rejected.

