11.3.1. Study Success Criteria

The study success will be determined █ for ACUITY X4 and RELIANCE 4-FRONT. Each study will be considered successful if all primary endpoints specific to that lead are passed

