1 PLANNED PROTOCOL ANALYSES

All information necessary to complete the required analyses for the NAVIGATE X4 study are contained within the NAVIGATE protocol. Additional information is found in the following section².

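### RELIANCE 4-FRONT shock conversion endpoint: Protocol 11.2.8.1 rejects the null on the upper confidence limit, 11.2.8.3 on the lower; only the lower limit tests the stated hypotheses

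*Protocol*

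**What the plan says.** Protocol 11.2.8.1 sets the hypotheses for VT/VF shock conversion with a RELIANCE 4-FRONT lead: the null is a conversion rate of 93% or less, the alternative a rate above 93%. It then states that the null is "rejected in favor of the alternative if the upper confidence limit of the observed percent of successful conversions is greater than 93" percent. It gives no confidence level and no interval method.

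Protocol 11.2.8.3, for the same endpoint, specifies a one-sided exact binomial test with a lower Clopper-Pearson limit. It rejects the null if the "lower one-sided 95% confidence limit for the conversion rate is greater than 93" percent.

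Two other RELIANCE endpoints have hypotheses of the same form, and both use the lower limit:

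- Primary Safety Endpoint 1 (11.2.1.3): "If the lower confidence limit exceeds 93%, the null hypothesis will be rejected".
- Primary Safety Endpoint 2 (11.2.3): "If the lower confidence limit exceeds 94%, the null hypothesis will be rejected".

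SAP section 1 adds no rule of its own: "All information necessary to complete the required analyses for the NAVIGATE X4 study are contained within the NAVIGATE protocol". The additional information in SAP section 2 does not mention this endpoint's test.

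**The concern.** The two subsections give opposite decision rules for one pair of hypotheses. Both sentences are current text and both are fully legible, so the conflict does not depend on anything redacted. Any result whose interval straddles 93% (lower limit at or below it, upper limit above it) is a success under 11.2.8.1 and a failure under 11.2.8.3.

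The endpoint is meant to confirm that the lead and its pulse generator can convert VT/VF, in a study that supports a pre-market submission. If the results fall in that band, the endpoint could be reported as met or not met depending on which subsection is cited, and that choice would be made after the data are known.

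**Working it through.** **Inputs.** The goal is p0 = 0.93, with null p ≤ 0.93 and alternative p > 0.93 (11.2.8.1). The interval is one-sided 95% Clopper-Pearson (11.2.8.3). The numeric alpha in 11.2.8.3 is blacked out, but the 95% one-sided limit implies 5%. The sample-size text in 11.2.8.2 is redacted and induction is optional (Protocol 10.5.12: "Subjects are not required to undergo induction testing"). The number of tests n is therefore an assumption, taken from 50 to 1000. There is no visible figure of the plan's own to reproduce.

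**Formulas.** For x conversions in n tests:

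- lower limit = Beta quantile at 0.05 with parameters (x, n − x + 1)
- upper limit = Beta quantile at 0.95 with parameters (x + 1, n − x)
- cut-off of each rule = smallest x whose limit exceeds 0.93
- P(pass) at true rate p = P(X ≥ cut-off), X ~ Binomial(n, p)

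**Worked case, n = 200.** With x = 180 (90.0% observed) the limits are 0.858 and 0.933, so 11.2.8.1 passes and 11.2.8.3 fails. With x = 192 the lower limit is 0.929, still a failure under 11.2.8.3. With x = 193 it is 0.935, a pass. Every result from 180 to 192 passes one section and fails the other.

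**Cut-offs and probability of passing** (U = upper-limit rule of 11.2.8.1, L = lower-limit rule of 11.2.8.3):

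| n | Cut-off U | Cut-off L | U, true 93% | L, true 93% | U, true 90% | L, true 90% |
|---|---|---|---|---|---|---|
| 50 | 43 (86.0%) | 50 (100%) | 97.8% | 2.7% | 88% | 0.5% |
| 100 | 89 (89.0%) | 98 (98.0%) | 95.3% | 2.6% | 70% | 0.2% |
| 150 | 134 (89.3%) | 145 (96.7%) | 96.6% | 4.5% | 67% | 0.2% |
| 200 | 180 (90.0%) | 193 (96.5%) | 95.8% | 2.7% | 56% | <0.1% |
| 300 | 272 (90.7%) | 287 (95.7%) | 95.0% | 3.8% | 40% | <0.1% |
| 500 | 455 (91.0%) | 475 (95.0%) | 96.3% | 4.3% | 25% | <0.1% |
| 1000 | 916 (91.6%) | 944 (94.4%) | 96.1% | 4.4% | 5% | <0.1% |

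A true rate of 93% is the null boundary, so those two columns are type I error rates. At every n the upper-limit rule accepts an observed rate below the goal. At a true 85% its false-pass chance is 52% (n = 50), 16% (n = 100) and 2.6% (n = 200).

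**How often the sections disagree.** Any result that passes L also passes U, so the chance of opposite answers is P(pass U) − P(pass L). At a true 93% and n = 200, for example, 95.8% − 2.7% = 93.1%.

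| True rate | n = 50 | n = 200 | n = 500 | n = 1000 |
|---|---|---|---|---|
| 93% | 95% | 93% | 92% | 92% |
| 95% | 92% | 79% | 45% | 17% |
| 97% | 78% | 25% | 0.5% | about 0 |

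**Sensitivity to the confidence level.** Because 11.2.8.1 states none, the upper-limit rule was repeated at 97.5% one-sided. Its pass rate at a true 93% is then 97.6% to 98.3%, so the conclusion is unchanged.

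**The case against.** The strongest reply is that 11.2.8.3 is already correct and complete. It names the test, the interval and the rejection rule, whereas 11.2.8.1 cannot be carried out without borrowing an interval method and level from 11.2.8.3. On that reading there is one specified analysis and one badly worded sentence, and the 95% to 98% error rates belong to an analysis nobody is likely to run. This largely stands as to cause: a slip is the natural explanation, and most statisticians would follow 11.2.8.3. It does not remove the conflict. The sentence stands with the formal hypotheses, and neither document says which subsection prevails.

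A second reply concerns size. The Protocol synopsis says every endpoint has at least 80% power. If that holds under the lower-limit rule, the two sections disagree at the design rate with probability at most 100% − 80% = 20%. That is fair. The design rate and planned n are redacted and testing is optional, so no single row above should be read as the expected impact.

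Third, the endpoint is secondary. Protocol 11.3.1 says: "Each study will be considered successful if all primary endpoints specific to that lead are passed". The primary decision is therefore untouched. Protocol 11.3.4 describes gated testing of secondary endpoints, but the RELIANCE order is not visible. Whether a pass here would open a further test cannot be determined.

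**Conclusion.** The concern holds. Protocol 11.2.8.1 is wrong as written, and 11.2.8.3 has the valid rule. Read literally, 11.2.8.1 has a type I error of 95.0% to 97.8% at the 93% boundary, against 2.6% to 4.5% for the lower-limit rule, over assumed n from 50 to 1000 with one-sided 95% exact limits. The contradiction itself rests on no assumption; only its size depends on n and the true rate.

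The weight is moderate: the point should be fixed, but it is probably a wording slip, it concerns a secondary endpoint, and it leaves the primary success decision for the lead unchanged.

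A related slip is editorial only. The tipping-point text in 11.1.3, 11.2.1.3 and 11.2.3 runs from "passing (null hypothesis) to failing (null hypothesis rejected"), the reverse of the labels in 11.1.4.3 and 11.1.5.3. It describes a sensitivity analysis and changes no endpoint result.

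**What to change.** In Protocol 11.2.8.1, replace *upper confidence limit* with *lower one-sided 95% confidence limit*, so that it agrees with 11.2.8.3. If the protocol is not to be reissued, record the correction in the SAP before the endpoint is analysed; Protocol 11.4.7 already provides for documenting changes there.

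At the same time, correct the tipping-point labels in 11.1.3, 11.2.1.3 and 11.2.3 so that passing means the null is rejected and failing means it is not, as in 11.1.4.3 and 11.1.5.3.

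The cost is wording only. The test, alpha, sample size and data collection do not change.
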